Can Topical Application of Tranexamic Acid Reduce Postoperative Blood Loss in Shoulder Arthroplasty and Primary Hip Arthroplasty?

NCT 0197559

May 8, 2018

Can Topical Application of Tranexamic Acid Reduce Postoperative Blood Loss in Primary Hip Arthroplasty?

PI: [name]

Co-Investigators: [name], [name],

[name], [name]

[figure not shown]
Investigation will be performed at the Steadman Hawkins Clinic of the Carolinas, Greenville, SC; Simpsonville, SC; Greer, SC

Specific Aim/Hypothesis: The objective of this study is to evaluate the efficacy of topical tranexamic acid in decreasing blood loss following primary total hip arthroplasty. We hypothesize that topical application of tranexaminic acid (TXA) prior to closure reduces postoperative bleeding as measured by absolute changes in postoperative hemoglobin levels and surgical drain output. In addition, use of topically applied tranexaminic acid may reduce the need for transfusions, the rates of hematomas, infections, and length of hospital stay.

Significance: Post-operative blood transfusion is often required and variable depending on primary, revision, or reverse procedures, with reported rates ranging from 8% to 45% in several studies. (Sperling, J JSES 2005) (Millet, P JBJS 2006). Following hip and knee arthroplasty, estimated blood loss ranges from 450-1500 ml and 180-330 ml, respectively (Bierbaum JBJS 1999).

TXA is an antifibrinolytic agent that has been studied extensively in major orthopaedic and cardiac procedures and has been found to efficacious in reducing blood loss and transfusion requirements. Applied either systemically or topically, TXA functions to decrease blood loss through the inhibition of clot degradation. Its mechanism of action is via a reversible interaction with plasminogen and the active protease, plasmin. TXA saturates the lysine binding site of plasminogen, inhibiting plasminogen from binding to the surface of fibrin. It has a relatively short half life (1-2h) and is rapidly excreted unchanged in urine (Eubanks, JAAOS 2010). TXA has been associated with nausea, vomiting, diarrhea, orthostatic reactions, and rare dermatitis reactions. No increased risk of

thromboembolism has been reported.

Topical application of tranexaminic acid to bleeding wound surfaces has been shown to reduce blood loss in patients undergoing major orthopaedic surgeries, without an increased risk of systemic complications. Numerous studies have shown that systemic use of TXA in hip and knee arthroplasty is safe and effective in reducing blood loss following hip or knee replacement (Sepah JOSR 2011) (Yang JBJS 2012). A recent RCT showed that topical TXA in knees could reduce post-operative bleeding by 20%-25%, or 300 to 400ml, resulting in roughly 16% higher postoperative hemoglobin levels compared to placebo (Wong JBJS 2010). In a recent meta-analysis investigating the effectiveness and safety of tranexamic acid in total knee arthroplasty, the amount of blood loss and the number of patients requiring blood transfusions was lower in patients receiving tranexamic. Similar results have also been demonstrated in posterior lumbar spine surgery (Endres BMC Surgery 2011). However, to date, no studies have shown the effectiveness of topical TXA application in primary hip arthroplasty procedures.

From a financial perspective, the application of TXA has many benefits. In one study, the use of TXA reduced the cost of blood salvage by as much as 25%, prompting the institution to eliminate routine use of intra-operative blood salvage (Cell Saver) in primary total hip and knee arthroplasty given its limited impact in patients treated with TXA (Irrison OTSR 2012). The same study suggested a cost-saving effect of TXA therapy related to decreases in anesthesia costs and length of hospital stays. Topical application of tranexaminic acid is simple and inexpensive compared with other commonly used topical fibrin sealants. Approximate costs for fibrin sealants from one study was \$585 US compared with a \$6 cost of administering TXA as noted in the Wong (JBJS 2010) article.

Double blind randomized prospective trial:

Sample Size Estimate: Provided by [name] PhD

Hip: Using a 2-tailed t-test for independent groups and post-op blood loss as the primary outcome measure with an estimated effect size of 0.59, at 80% power, a standard error of 0.05, and a drop-out rate of 20%, we estimate the need for a minimum sample size of 100 (50 in each group) for statistical significance and 120 to account for the drop outs. The study will use an intention to treat analysis.

Current Standard Of Care: Non Study Patients undergoing a THA may receive TXA intravenously depending on their surgeon's current standard of care. This decision is made on a case by case basis depending on their surgeon's standard of care. Intravenous application is approved by GHS. The study treatment arms will not change, however potential patients will be informed of the standard of care as well as the randomization options. The topical application may offer less risk or a more direct effect to patients as compared to the intravenous application.

Age and Gender Matched Control (Intravenous TXA) Group: A group of patients who previously received TXA intravenously and have completed the same standard post-operative protocol will be age and gender matched to the study participants who were randomized to the topical TXA group for comparison. Using a 2-tailed t-test for independent groups and post-op blood loss as the primary outcome measure with an estimated effect size of 0.55 at 80% power, a standard error of 0.05, and no drop outs, we estimate the need for a minimum single arm sample size of 53 for statistical significance. The study will use an intention to treat analysis.

Inclusion Criteria: .

Hips: All adult patients over the age of 18 scheduled for a primary total hip arthroplasty will be eligible for the inclusion in the study.

Exclusion Criteria:

The exclusion criteria will include allergy to TXA, refusal of blood products, preoperative use of anticoagulant therapy within 5 days of surgery, history of seizures, renal failure (creatine clearance <30ml/min), bleeding disorders, venous thromboembolism (deep vein thrombosis and/or pulmonary embolism), significant cardiac history (myocardial infarction, angina, stroke, lower limb ischemia), or perioperative anemia (hemoglobin <11g/dl in females and < 12g/dl in males).

At the time of surgery, via randomization patients will receive either:

- 1) **Control:** Irrigation of 100ml of normal saline
- 2) **TXA:** 1g (100mg/ml) of tranexaminic acid (Cyklokapron) Pfizer, New York,NY in 100ml normal saline solution. This dosage was chosen as this has been utilized in previous studies and was shown to be safe and effective in reducing blood loss following total knee arthroplasty (Craik Eur J Orthop Surg Traumatol 2013). Effective TXA dosing has shown to range from 1-1.5g, with 1 g being the most cost effective to the patient. A higher dose of 3g was also used in a study and no difference in efficacy was observed. (Wong JBJS 2010). The solution will be prepared by our surgical pharmacy and provided at the time of surgery to the operative circulating staff. Both the patient and the surgical staff will be blinded as to the treatment regimen.

Surgical Intervention:

After all components are secured into place, the joint will be thoroughly irrigated and the study medication applied to open joint surfaces with use of a bulb syringe, solution soaked sponges will be left in contact with the tissues for five minutes, and then removed. The wound will then be closed without any irrigation or manipulation. Surgical drains will be placed for <24 hours. Postoperatively, all patients will receive aspirin, Coumadin, or LMWH (Low molecular weight heparin) based on our current thromboprophylaxis protocols).

Outcome Measures

Primary outcome will be blood loss as calculated from the difference between the preoperative hemoglobin and the lowest postoperative hemoglobin during the hospital stay or the lowest postoperative hemoglobin prior to blood transfusion. Based on hemoglobin balance, the estimated blood loss will be calculated according to the formula described by Good et al.² and Nadler et al.²³

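### Read literally, the past intravenous TXA group admits only patients who completed the post-operative protocol while the topical group admits all randomised, which could make intravenous TXA look safer

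*Combined protocol and SAP*

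**What the plan says.** The paragraph headed Age and Gender Matched Control (Intravenous TXA) Group forms a non-randomised comparator from "A group of patients who previously received TXA intravenously and have completed the same standard post-operative protocol". These patients are to be "age and gender matched to the study participants who were randomized to the topical TXA group for comparison". The group is sized on blood loss with "no drop outs, we estimate the need for a minimum single arm sample size of 53 for statistical significance", and the paragraph closes with "The study will use an intention to treat analysis".

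The randomised comparison, under Sample Size Estimate, is also by intention to treat but allows for "a drop-out rate of 20"%. No completion condition is placed on the topical arm.

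Just before the intravenous group is introduced, the Current Standard Of Care paragraph says: "The topical application may offer less risk or a more direct effect to patients as compared to the intravenous application". The Outcome Measures section lists complications (haematoma, infection, revision and thromboembolism among them) as data to be collected and compared. It does not say between which groups. It also does not say how complications are to be found, or over what period.

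**The concern.** Completing a post-operative protocol is something that happens after treatment. If it is a condition of entry for one group and not the other, the groups differ by selection as well as by route of administration. Age and gender were fixed before surgery, so matching on them cannot correct this.

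The safety data are where it could matter. A patient who died, was transferred or had an early revision may plausibly not complete the protocol. Such a patient would be left out of the intravenous group but kept in the topical group. The randomised control is saline, so the intravenous group is the only part of the study in which the two routes can be set side by side. A comparison of complications there could make topical TXA look less safe than it is, or hide a real advantage.

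The planned blood-loss test is less exposed. Its outcome is taken from haemoglobin during the hospital stay, so later non-completion reaches it mainly through who is admitted to the intravenous group.

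**Working it through.** **1. The plan's own figure.** Inputs from the intravenous paragraph: "an estimated effect size of 0.55 at 80% power", a two-sided t-test for independent groups, and "a standard error of 0.05", read here as the significance level. The normal approximation is n = 2(1.960 + 0.842)² / 0.55² = 15.70 / 0.3025 = 51.9, so 52 per group. The t-test calculation gives 52.87, so 53, with 80.1% power at 53 per group. The stated 53 reproduces. Completion of the protocol is not an input to it.

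**2. The entry rules side by side.**

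| | Topical group | Intravenous group |
|---|---|---|
| Entry decided by | Randomisation | Past intravenous TXA and completion of the post-operative protocol |
| Drop-out assumed | 20% | None |
| Analysis named | Intention to treat | Intention to treat |

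The last line does not fit the right-hand column. A group restricted to completers has already lost the patients whom intention to treat is meant to keep.

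**3. Illustration of size.** Let p be the true complication rate, equal in both groups. Let q1 and q0 be the probabilities of not completing with and without a complication. The rate seen among completers is

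p(1 − q1) / [p(1 − q1) + (1 − p)(1 − q0)].

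The denominator is the overall completion rate. Holding overall non-completion at 20% makes it 0.80, so the observed rate is p(1 − q1)/0.80. If every topical event is captured, the apparent topical-to-intravenous ratio is 0.80/(1 − q1), whatever the value of p.

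The documents give neither p nor q1, and the 20% is borrowed from the randomised arms. All three are assumptions. With p = 5%:

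| q1 | Rate among intravenous completers | Expected events in 53 | Apparent ratio |
|---|---|---|---|
| 20% | 0.05 × 0.80 / 0.80 = 5.0% | 2.65 | 1.00 |
| 50% | 0.05 × 0.50 / 0.80 = 3.1% | 1.66 | 1.60 |
| 80% | 0.05 × 0.20 / 0.80 = 1.25% | 0.66 | 4.00 |

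**4. What would reduce or reverse it.** If patients with complications complete more often than others, the direction changes: at q1 = 10% the ratio is 0.80/0.90 = 0.89. If a fraction m of topical events is missed after drop-out, the ratio is multiplied by (1 − m). At q1 = 50% and m = 20% (assumed) it falls from 1.60 to 1.60 × 0.80 = 1.28, and at m = 37.5% it reaches 1.00.

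**The case against.** The strongest reply is that the plan specifies no safety comparison with the intravenous group. The only outcome named for that group is blood loss, and the study's aim and hypothesis do not mention intravenous TXA. The sentence about less risk is background, placed beside what prospective patients will be told. This stands: a topical-versus-intravenous comparison of complications is implied by the general list under Outcome Measures, not stated.

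The second reply is that completing the protocol is undefined and may mean only having gone through the same care pathway. On that reading nobody is excluded for a later event. This stands as a possible meaning. It is not what the words say, though, and the change of wording would then record the intended meaning.

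A reader might also infer more than the documents support:

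- **That the intravenous group is depleted of events.** This needs non-completion to be more common after a complication, and no figure on that is given.
- **That the topical group is complete.** Intention to treat keeps drop-outs in the denominator, but no rule covers events after drop-out.
- **That topical patients are questioned about complications at study visits while intravenous events come from charts.** The visit schedule is attached to function and pain, and no method of ascertainment is given for either group.
- **That a true 5% rate would fall to 2.6% when half of patients with a complication do not complete.** That figure, 0.05 × 0.5 / (1 − 0.05 × 0.5), assumes every event-free patient completes, which does not sit with 20% overall non-completion.

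Finally, a past cohort of 53, matched on two variables and treated intravenously at the surgeon's discretion, could not settle relative risk even with perfect entry rules. That is correct, and is why the result should be called descriptive.

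**Conclusion.** The point holds in a limited form. As worded, entry to the intravenous group depends on the post-operative course and entry to the topical group does not. This is a stated rule that can bias a comparison, not merely a missing detail.

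The likely direction, towards intravenous TXA looking safer, rests on patients with complications being less likely to complete. Under the illustrative assumptions the apparent ratio between groups with equal true rates runs from 1.00 to 4.00. In patients, the difference is one or two expected events among 53. With non-completion unrelated to complications there is no bias, and under-counting after topical drop-out would shrink it. The actual size cannot be calculated from the documents.

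The documents do not support saying that the randomised comparison with saline is affected, or that a planned safety objective has failed. The point is a cheap improvement to make before the intravenous group is assembled.

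**What to change.** In the intravenous paragraph, replace *have completed* with *were managed under* the same standard post-operative protocol. Enter eligible intravenous patients by operation date, whatever happened afterwards. For complications, state one observation window and one set of record sources, and apply both to the topical and intravenous groups. Report this non-randomised safety comparison as descriptive.

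The cost is a change of wording and one rule for abstracting records. The 53 does not change, because completion plays no part in its calculation. The small downside is that some intravenous patients will have incomplete later follow-up, and the number and extent must be reported.

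### The comparison of randomised topical TXA with a historical IV cohort rests on an unadjusted t-test, carries an intention-to-treat label that cannot apply to that cohort, and is not ranked below the randomised comparison.

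*Combined protocol and SAP*

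**What the plan says.** The paragraph headed Age and Gender Matched Control (Intravenous TXA) Group takes patients treated earlier with IV TXA who "have completed the same standard post-operative protocol". They "will be age and gender matched to the study participants who were randomized to the topical TXA group for comparison". The comparison is then sized: "Using a 2-tailed t-test for independent groups and post-op blood loss as the primary outcome measure with an estimated effect size of 0.55", with 80% power and "a standard error of 0.05, and no drop outs", which leads to this: "we estimate the need for a minimum single arm sample size of 53 for statistical significance". The paragraph ends by stating that the study will be analysed by intention to treat.

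The Sample Size Estimate for the randomised topical versus saline comparison uses the same test and parallel wording: "post-op blood loss as the primary outcome measure with an estimated effect size of 0.59".

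The protocol has no separate analysis section, so the t-test in these sizing sentences is the only test named for either comparison. Nothing is said about covariate adjustment, about a matched analysis, or about which comparison ranks first. The Current Standard Of Care paragraph says that IV use outside the study depends on the surgeon and is decided patient by patient.

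**The concern.** Three features of the IV comparison need attention together.

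- **Confounding.** Past patients received IV TXA at their surgeon's discretion. Matching on age and gender does nothing direct about preoperative hemoglobin, body size, ASA class, cementing, surgeon or calendar period. An unadjusted t-test takes any resulting difference in blood loss as a treatment effect.
- **Selection.** The topical side is defined by randomisation. The IV side is defined afterwards, by earlier treatment and completion of the post-operative protocol. The paragraph does not say that the trial's exclusion criteria apply to IV patients. Intention to treat has no clear meaning for a group that was never assigned.
- **Rank.** Blood loss is called the primary outcome measure again for this comparison, at the same 0.05, with no statement that it is subordinate to the randomised one.

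At stake is a topical versus IV result that reads as a randomised finding and is not one.

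**Working it through.** **Inputs from the protocol.** Standardised effect 0.55, two-sided independent-groups t-test, 80% power, 53 in the IV arm. The 0.05 is written as a standard error. I read it as the significance level, because 53 then reproduces.

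**Inputs assumed.** Bias of 0.1 to 0.3 SD and within-pair correlation r of 0 to 0.3. The documents give neither.

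**1. The plan's own figure.** Solving the noncentral t power equation for effect 0.55, two-sided 0.05 and 80% power gives n = 52.87 per arm, rounded up to 53. Power at 53 per arm is 80.1%. The stated 53 is therefore an independent-groups calculation that takes no account of the matching.

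**2. What bias does to the test.** With no true difference but a bias of b SD, the t statistic has noncentrality b × √(53/2) = b × 5.148 on 104 degrees of freedom.

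| Assumed bias (SD) | Noncentrality | Probability of p < 0.05 |
|---|---|---|
| 0 | 0 | 5.0% |
| 0.1 | 0.515 | 8.0% |
| 0.2 | 1.030 | 17.5% |
| 0.3 | 1.544 | 33.4% |

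For scale, 0.2 SD is 0.2/0.55 = 36% of the effect the comparison is designed to detect.

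**3. What ignoring the matching does.** This applies only if patients are matched individually. With within-pair correlation r ≥ 0, the independent-groups standard error is too large by the factor 1/√(1 − r), and the actual size of the test is 2 × [1 − Φ(1.96/√(1 − r))].

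| Assumed r | SE too large by | Actual size | Power of paired test, 53 pairs |
|---|---|---|---|
| 0 | 0% | 5.0% | 79.4% |
| 0.1 | 5.4% | 3.9% | 83.4% |
| 0.2 | 11.8% | 2.8% | 87.4% |
| 0.3 | 19.5% | 1.9% | 91.3% |

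The error is towards caution: intervals are too wide and false positives become fewer. The independent-groups test keeps its planned 80% power at every r of 0 or more.

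**4. Variables for adjustment.** Outcome Measures requires preoperative hemoglobin and lists age, weight, ASA class and cemented versus non-cemented among the data to be collected and compared. Gender is already needed for the matching. For trial patients, adjustment needs nothing new.

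**The case against.** The strongest defence is that the t-test appears only in sizing sentences. Sizing on independent groups is a common, slightly conservative convention and need not be the final model. That is fair as far as it goes, but no other model is given, so the t-test is the only analysis the plan specifies.

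The statement that past patients completed the same protocol may mean only that they were treated under the same pathway. That reading is possible, and the documents give neither direction nor size for a completion effect. The wording still permits selection on completion and should be settled.

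The plan never says that the matching is in pairs. The topical arm is 50 (60 with dropouts) against 53 IV patients, so the counts do not pair off exactly. Under group matching there would be no pairs to analyse. This stands, and it is why the standard error is a minor point here.

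A reader might also infer that the IV comparison is a second primary hypothesis and that two 0.05 tests sharing the topical arm carry about 9% familywise error. The documents do not support this.

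- Co-primary status is not declared: the Specific Aim omits IV TXA, and no rule lets either comparison carry the trial.
- The arithmetic gives 9.07% only if saline, topical and IV are all equivalent. The Significance section says systemic TXA reduces blood loss. If IV differs from saline, at most one of the two nulls can be true, and chance error stays at or below 5%.
- The figure needs full 5% size in both tests. With individual matching, the planned unpaired test would bring it to 8.2% at r = 0.1 and 6.6% at r = 0.3, even with all three treatments equal.

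**Conclusion.** The point holds as one about bias, labelling and rank. The plan specifies only an unadjusted independent-groups t-test for a non-randomised historical cohort, applies an intention-to-treat label that cannot hold there, and leaves the rank of the comparison unstated. Under an assumed bias of 0.1 to 0.3 SD, the test rejects a true null about 8% to 33% of the time. These figures show how sensitive the test is. They do not estimate the bias actually present, which the documents do not allow one to judge.

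The loss of precision from ignoring the matching is secondary: 5% to 20% on the standard error at assumed correlations of 0.1 to 0.3, nil at 0, and relevant only to individual matching. It should not be read as a source of false positives, and no familywise error figure should be attached to this point. The randomised topical versus saline comparison is unaffected. The change is worth making because it is cheap and removes a route to a misleading claim.

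**What to change.** 1. State that topical versus saline is the only primary comparison. Make topical versus IV secondary, reported as an estimate with a 95% CI.
2. Analyse topical versus IV by regression of blood loss on group with age, sex, preoperative hemoglobin, weight, ASA class and cementing. If matching is individual, say so and cluster the standard errors on matched set.
3. Select IV patients by the trial's inclusion and exclusion criteria, whether or not they completed the post-operative protocol.
4. Remove the intention-to-treat label for the IV cohort and define its analysis set. Keep the label for the randomised comparison.

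The cost is a few lines of text, slightly more analysis, and abstraction of the same variables and eligibility criteria from the IV patients' charts. The IV comparison can no longer be claimed as primary. Adjustment will not remove confounding by unmeasured factors, which is a further reason for its secondary rank.
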